13.3 Safety Analysis

Safety will be evaluated on the basis of treatment-emergent AEs (TEAEs), vital signs, weight, physical examinations, tumor assessments, and clinical laboratory assessments.

All adverse events will be coded by Preferred Term and System Organ Class using the most recent version of MedDRA. The National Cancer Institute Common Terminology Criteria for Adverse Events (CTCAE) (Version 5.0) will be used to grade both clinical and laboratory AEs. By-patient listings of deaths, SAEs, and AEs leading to discontinuation will be provided. The by-patient AE data listings will include onset and resolution dates, verbatim term, Preferred Term, treatment, severity (grade), relationship to treatment, action taken for the event, and outcome.

The incidence of treatment-emergent AEs (TEAEs) will be summarized by treatment group and tabulated by System Organ Class (SOC) and Preferred Term (PT). A TEAE is defined as an AE that first occurs or worsens in severity on or after the first dose of the study medication.

Vital signs (systolic and diastolic blood pressure, pulse, and temperature) and body weight will be summarized for each treatment group using descriptive statistics. Summary statistics (n, mean, median, standard deviation, minimum, and maximum) will be calculated for both the actual value and the change from baseline value at each scheduled visit.

Clinical laboratory data will be presented for each treatment group using descriptive statistics based on the observed values and change from baseline values at each scheduled visit. Summary statistics (n, mean, median, SD, minimum, and maximum) will be calculated for quantitative safety data and frequency counts will be compiled for classification of qualitative safety data. Shift tables from baseline to the worst post-baseline values during the treatment period will be provided for chemistry parameters and hematology parameters that have NCI-CTCAE v5.0 toxicity grades. Both scheduled and unscheduled post baseline values during the treatment period will be considered. Additionally, the number and percentage of patients with Grade ≥ 3 will be presented for each CTCAE gradable laboratory test.

All clinical laboratory data will be listed by patient. Values outside the normal ranges will be flagged and toxicity grades will be displayed for relevant parameters.

Pre-study abnormalities and reported abnormalities at the end of study will be tabulated by body system. Changes in physical examinations will be described in the text of the final study report. Tumor response assessments at each follow-up visit will be tabulated by treatment group.

Prior and concomitant medications will be tabulated for each treatment group; details regarding dose regimens and start/stop dates will be presented in by-patient data listings.

Progression Free Survival (PFS) defined from the time of registration to the time of the first radiographic documentation of objective progression (per RECIST v1.1) or the date of death, whichever is earlier, will be evaluated using Kaplan-Meier methods. Subjects still alive without progressive disease at the time of analysis will be censored on the date of the last objective progression-free observation prior to the start of subsequent anti-cancer therapy.

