 - A *brief* physical exam, to include ECOG status, by a Radiation Oncologist and/or Medical Oncologist and/or ENT or Head & Neck Surgeon must be done weekly during Pre-Treatment, Combination Treatment, and during the Mucositis Observation Follow-up until OM grade ≤ 1 is achieved.
6. Oral Mucositis Assessment will be performed by a trained on-site assessor at screening, day 1 prior to start of RRx-001 pretreatment, day 15 prior to the start of Combination Treatment (chemoradiation), twice a week (no less than 48 hours apart) during Combination Treatment (weeks 1 - 7), and once each week on the same day (± 1 day) during the Mucositis Observation Follow-up until an OM grade ≤ 1 is achieved. Lesions will be scored by a central assessor according to WHO ([Appendix C](#)) and WHO grade assessment will be communicated back to site study team by the central assessor.
7. Oral Mucositis Daily Questionnaire (OMDQ) to be completed in clinic at screening and then daily in the provided OMDQ Booklet starting Week 1 (protocol Day 15) of combination treatment, continuing through the Mucositis Observation Follow-up until an OM grade ≤ 1 is achieved. See [Appendix D](#).
8. Record current oral routines (i.e. smoking and chewing tobacco) at screening. If oral routines change, please update oral assessment accordingly. Review patient oral care instructions ([Appendix G](#)) and dispense oral hygiene kit following enrollment and prior to start of chemoradiation.
9. Lab Assessments include a Complete Blood Count (CBC) with differential, a Complete Metabolic Panel (CMP), magnesium and phosphate: to be performed at screening, weekly during Pre-Treatment, Combination Treatment, 28 Day Safety Visit, and as clinically indicated per institutional guidelines. CMP to include: sodium, potassium, glucose, calcium, albumin, bilirubin, ALT, AST, and Alk Phos.
10. Negative serum or urine pregnancy test required within 14 calendar days prior to start of treatment for women of childbearing potential.

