Study Design	This is a Phase 2a, randomized, open-label, parallel group trial to assess the safety and efficacy of three schedules of RRx-001 compared to standard of care in patients receiving a standard regimen of tri-weekly cisplatin plus concomitant IMRT in patients being treated for cancers of the oral cavity or oropharynx. Patients meeting the eligibility criteria and consenting to participate will be randomized 1:1:1:1 to one of the three regimens of RRx-001 or a control (~10 patients per arm) with 1 stratification factor (two levels: oral cavity or oropharynx): Arm 1: "RRx-001 Pre-Treatment + SOC Chemoradiation" Two infusions of RRx-001 will be given each week during the two weeks prior to the start of chemoradiation (four doses total). No additional RRx-001 will be given during chemoradiation. Arm 2: "RRx-001 Pre-Treatment + 2 Concurrent Doses + SOC Chemoradiation" Two infusions of RRx-001 will be given each week during the two weeks prior to the start of chemoradiation. In addition, one dose of RRx-001 will be given on the last radiation day in each of weeks 2 and 5 during chemoradiation Arm 3: "RRx-001 Pre-Treatment + 6 Concurrent Doses + SOC Chemoradiation" Two infusions of RRx-001 will be given each week during the two weeks prior to the start of chemoradiation. In addition, one dose of RRx-001 will be given on the last radiation day of each of the first 6 weeks during chemoradiation Arm 4: "SOC Chemoradiation Only (Control)" No doses of RRx-001 will be administered. Patients assigned to this arm will receive only standard of care chemoradiation

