Patients with radiation-induced mucositis generally show highly consistent clinical courses. Concomitant chemotherapy increases both the risk and severity of mucositis. Signs and symptoms typically begin by the completion of the first week of treatment (cumulative radiation dose of 10 Gy) and consist primarily of mucosal erythema and symptoms akin to a burned mouth from hot food or drink that are easily controlled with standard OTC pain medications. At cumulative radiation doses of 20 Gy to 30 Gy, the integrity of the mucosa breaks down and mucosal ulcerations that are usually limited to the movable mucosa (the more keratinized epithelium of the hard palate, dorsal tongue and gingiva are unaffected), occur. Unlike common oral ulcers like aphthous stomatitis, the ulcers associated with mucositis are irregular, deep and disproportionately painful, requiring more aggressive symptom management such as the use of narcotic analgesia. Ulceration severity usually peaks at radiation doses of around 50 Gy (end of week 5). The lesions expand and become confluent. Breakthrough pain, even with morphine or fentanyl is not uncommon. Lesions typically heal spontaneously after 2-4 weeks following the cessation of radiation therapy.

A variety of scales are used to assess mucositis severity, of these, the WHO scale is the most consistent and widely used. This scale, which has been effectively used in clinical trials, is based on a combination of functional (ability to eat) and objective (presence of ulceration or erythema) criteria. WHO scores correlate with patient-reported outcomes, analgesic use and resource use. Other available scales include RTOG and NCI-CTCv5, which have evolved to contain elements that are similar to WHO criteria.

Concepts of the pathogenesis of mucositis have undergone dramatic revisions from Sonis' original hypothesis in 1998 of epithelial injury due to direct clonogenic cell death of epithelial

stem cells to a complex biologic process involving oxidative stress and immune activation that culminates in epithelial apoptosis, atrophy, ulceration and healing [[Sonis 1998](#)].

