No doses of RRx-001 will be administered. Patients assigned to this arm will receive only standard of care (SOC) chemoradiation in the form of cisplatin either every three weeks (100 mg/m² for 3 doses) or weekly (40 mg/m² for 7 doses) and IMRT administered daily (excepting weekends) for 7 weeks.

Administration of RRx-001 will not be blinded, so patient and study staff may be aware of the treatment assignment.

Patients will be followed for safety endpoints throughout the study. Patients will be evaluated for the presence and severity of oral mucositis during the course of chemoradiation and for up to 6 weeks following the cessation of RT.

Oral mucositis (OM) will be evaluated according to [Section 11.1](#).

Patients in the study will be followed up to one year following the end of radiotherapy, in order to evaluate safety and tumor outcomes.

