12.1 Specification of Safety Variables

Safety assessments will consist of monitoring and reporting adverse events (AEs) and serious adverse events (SAEs) that are considered related to RRx-001, cisplatin or radiation therapy, all events of death, and any study specific issue of concern.

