12.2.1 Adverse Event Reporting Period

The study period during which all AEs and SAEs must be reported begins after informed consent is obtained and ends 30 days following the last administration of study treatment (RRx-001, cisplatin and radiation therapy) or study discontinuation/termination, whichever is earlier. After this period, investigators should only report SAEs that are attributed to prior study treatment.

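### Section 13.3 sets no TEAE start that exists in all four arms, so the by-arm TEAE table rests on unequal windows; the effect is small and the remedy cheap

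*Combined protocol and SAP*

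**What the plan says.** Section 13.3 (Safety Analysis) states that "The incidence of treatment-emergent AEs (TEAEs) will be summarized by treatment group", by system organ class and preferred term. The start rule is: "A TEAE is defined as an AE that first occurs or worsens in severity on or after the first dose of the study medication". The section gives no end to the TEAE window and no separate rule for the control arm.

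Section 6.1 says of Arm 4: "No doses of RRx-001 will be administered". Section 2 says of Arm 1: "Two infusions of RRx-001 will be given each week during the two weeks prior to the start of chemoradiation (four doses total". Arms 2 and 3 have the same lead-in and then 2 or 6 further doses during chemoradiation. Footnote 6 of the Schedule of Assessments (Section 1.2) dates the end of the lead-in: "day 15 prior to the start of Combination Treatment (chemoradiation".

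Two other passages bear on what can be counted. Section 12.2.1 says that the reporting period for all AEs "begins after informed consent is obtained and ends 30 days following the last administration of study treatment (RRx-001, cisplatin and radiation therapy"), or at study discontinuation or termination if that is earlier. The schedule marks adverse events at Weeks -2 and -1 without restricting them to any arm. Section 12.1 is narrower and describes reporting of events "that are considered related to RRx-001, cisplatin or radiation therapy".

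**The concern.** A by-arm incidence table is read across its columns, and that reading assumes that each column had the same opportunity to collect events. Here the start depends on a dose that one arm never receives, and the documents allow two meanings of the term.

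- **RRx-001.** Section 8.1.2 calls RRx-001 the study drug. On this meaning Arm 4 has no first dose, and its TEAE column is empty by definition.
- **Study treatment as listed in Section 12.2.1.** Arms 1-3 open at the first lead-in dose. Arm 4 opens at its first cisplatin or radiation.

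Neither meaning gives a common start, and no other section supplies one.

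Safety and tolerability of the RRx-001 schedules is the first stated objective, and Arm 4 is the only concurrent reference. The lead-in is when RRx-001 is given without chemoradiation: 4 of 4 doses in Arm 1, 4 of 4 + 2 = 6 in Arm 2, and 4 of 4 + 6 = 10 in Arm 3. Counting lead-in events in those arms is right, because they occur on drug. The flaw is that unrelated background events in the same period have no control counterpart to set them against.

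**Working it through.** The plan states no TEAE figure to reproduce, so the check counts the windows and then sizes the excess that would appear with no drug effect. It uses the Section 12.2.1 meaning of the term.

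**Inputs.** From the documents: Day 1 for the start of the lead-in and Day 15 for chemoradiation (Section 1.2, each ±2 days), radiotherapy lasting 6 to 7 weeks (Section 1.2, footnote 15), and about 10 patients per arm (Section 2). Assumed: Arm 4 follows the same calendar, there are no treatment breaks, the last fraction falls on the fifth day of the last week, and the window ends 30 days after the last study treatment as in Section 12.2.1.

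**Windows.**
- 7-week radiotherapy: last fraction 15 + 6×7 + 4 = Day 61; end 61 + 30 = Day 91. Arms 1-3: 91 days. Arm 4: 91 - 15 + 1 = 77 days.
- 6-week radiotherapy: last fraction 15 + 5×7 + 4 = Day 54; end 54 + 30 = Day 84. Arms 1-3: 84 days. Arm 4: 84 - 15 + 1 = 70 days.

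The difference is 14 days in both cases. A 28-day end, the period named in the safety objective, gives 89 v 75 or 82 v 68, again 14 days apart.

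**Excess per event term.** Let p be the control incidence of a term, and let the lead-in background rate be k times the later rate. With a constant rate within each period, cumulative exposure in Arms 1-3 relative to Arm 4 is

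r = (77 + 14k)/77 or (70 + 14k)/70,

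and with no drug effect the incidence in Arms 1-3 is 1 - (1 - p)^r. The excess in patients per arm of 10 is 10 × [1 - (1 - p)^r - p].

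The documents give no background rate, so k is an assumption and is shown over a range. The first figure in each cell is for 7-week and the second for 6-week radiotherapy.

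| k | r | Largest excess over all p | p = 0.10 | p = 0.30 |
|---|---|---|---|---|
| 0.1 | 1.018 / 1.020 | 0.066 / 0.073 | | |
| 0.25 | 1.045 / 1.050 | 0.164 / 0.179 | 0.043 / 0.047 | 0.113 / 0.124 |
| 0.5 | 1.091 / 1.100 | 0.320 / 0.350 | | |
| 1 | 1.182 / 1.200 | 0.614 / 0.670 | 0.171 / 0.188 | 0.440 / 0.482 |

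The largest excess falls at p of about 0.60 to 0.63. Worked example (7-week, k = 1, p = 0.10): r = 91/77 = 1.182; 1 - 0.90^1.182 = 0.1171; 10 × (0.1171 - 0.10) = 0.171.

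If a Week 7 cisplatin dose on Day 57 follows 6-week radiotherapy, the end is Day 87, the windows are 87 v 73 days, and the largest excess at k = 1 is 0.645, inside the range above.

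**Which k is plausible.** Common terms are likely to be chemoradiation toxicities, which start after Day 15. Section 3.1 says of mucositis: "Signs and symptoms typically begin by the completion of the first week of treatment (cumulative radiation dose of 10 Gy". For such terms the lower values of k are more likely.

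**Cross-check on any event.** At an assumed constant background rate of 0.1, 0.25, 0.5 or 1.0 AE per patient-month in every arm, incidence with 7-week radiotherapy is 26.2% v 22.6%, 53.2% v 47.4%, 78.1% v 72.3% or 95.2% v 92.3%. The excess is about 3 to 6 points, or 0.3 to 0.6 patients per 10.

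**The case against.** The strongest reply is that this is a missing definition in a small exploratory study, with little consequence. Most of it stands. Section 13.3 only summarizes TEAEs, and no test on them is planned. The excess is under one patient per term and overstates RRx-001 toxicity rather than hiding it. By-patient listings carry onset dates, so the periods can be separated at analysis. Grade 3 or higher laboratory counts, the named-toxicity tabulations, tumor response and PFS do not use the TEAE rule.

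Several stronger inferences are tempting and are not supported:

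- **That the plan lays down a 14-day asymmetry.** It does not. The 14 days follow from one of two meanings of an undefined term.
- **That control events in the two lead-in weeks are discarded by rule.** This needs Arm 4 to wait out those weeks untreated. The schedule shows Weeks -2 and -1 without arm restriction, but Section 2 ties the baseline assessment to the first day of RRx-001, and the schema in Section 1.1 is not reproduced in the text available. If Arm 4 starts chemoradiation promptly, no control events are lost, although Arms 1-3 still have a window about 14 days longer.
- **That the window end is settled.** Section 12.2.1 bounds AE reporting, not TEAEs, and allows an earlier end at discontinuation; the objectives refer to 28 days. The window lengths rest on an assumption, while the difference between arms does not depend on the common end chosen.
- **That several patients per arm would be spuriously affected.** At the assumed rates in the cross-check, 0.5 to 3.7 of 10 patients would have some background event in the lead-in. Many of them would have an event later anyway, so the whole-window excess stays at about 3 to 6 points.

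What the reply does not remove is that neither meaning of the stated rule gives the four arms the same window.

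**Conclusion.** The point holds and is minor. As written, the TEAE rule gives Arm 4 either no start at all or a start about 14 days later, relative to chemoradiation, than in Arms 1-3. On the second meaning the spurious excess is at most about 0.07 to 0.67 patients per term per arm of 10, always toward more events on RRx-001, with the lower end more likely for common terms. That size rests on the assumed lead-in rate, constant rates within periods, the Section 12.2.1 end, and Arm 4 following the Day 1 to Day 15 calendar. The documents do not support a claim that the table would produce a false safety signal or affect any planned test. The case for acting is that the choice between meanings is better made before the data are seen.

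**What to change.** In Section 13.3:

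- Define the TEAE start in every arm as protocol Day 1: before the first RRx-001 dose in Arms 1-3, and the same scheduled Week -2 Day 1 in Arm 4.
- State the window end as in Section 12.2.1: 30 days after the last study treatment, or discontinuation or termination if earlier.
- Split the by-arm TEAE table into lead-in (before chemoradiation) and chemoradiation-onward periods. Make the second the equal-window comparison with control: 77 days in every arm for 7-week radiotherapy, 70 for 6-week.
- If Arm 4 does not observe the two-week lead-in, use only the chemoradiation-onward period for the comparison with control, and show the lead-in events of Arms 1-3 separately without a control column.
- State that Section 12.2.1 (all AEs from consent) governs AE collection in Arm 4 over the narrower wording of Section 12.1. A control patient in the lead-in has not yet received any of the treatments to which Section 12.1 refers.

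Moving every arm to chemoradiation start without the split would equalize the windows but drop all of Arm 1's dosing period from the table.

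The cost is a revised definition and one extra table split. No new data are needed if Section 12.2.1 is followed. The lead-in comparison does depend on complete recording of control AEs in those two weeks.

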11. Chest CT scan, or PET/CT scan, must be done within 42 calendar days prior to starting treatment to rule out metastatic disease. Chest CT scan, or PET/CT scan, imaging during Long-Term Follow-Up to be performed per institutional standards and assessed via RECIST v1.1 until progression (PD) or start of next cancer directed therapy or 12 month post RT visit, whichever occurs first. When measurable disease is not present (e.g. post-operative patients), RECIST v1.1 assessment is not performed until measurable disease presents (considered PD) or start of next cancer directed therapy.
12. CT scan, MRI, or PET/CT scan of the tumor site and neck nodes must be done within 42 calendar days prior to starting treatment. Note: The CT scan of the neck and/or PET/CT performed for radiation planning may serve as both staging and planning tools. Imaging evaluations of the primary tumor and neck should be performed via institutional standards and assessed via RECIST v1.1 until progression or start of next therapy. When measurable disease is not present (e.g. post-operative patients), RECIST v1.1 assessment is not performed until measurable disease presents (considered PD) or start of next cancer directed therapy. The post-radiation imaging can be contrast enhanced CT, MRI, or PET/CT of the head and neck, or whole body PET/CT (minimum neck and chest), based on the preference of the treating clinician.
13. Administration of RRx-001 to be performed according to the schema [Section 1.1](#) and [Section 8.1.2](#), with pre-medications as described in the pre-medications [Section 8.1.5](#).
14. For Cisplatin dosage, refer to [Section 8.2](#).
15. Radiation Therapy (IMRT) will consist of single daily fractions of 2.0 to 2.2 Gy with a cumulative radiation dose between 60 Gy and 72 Gy, lasting 6 to 7 weeks in duration.
16. Combination Treatment will be a duration of 6 to 7 weeks depending on IMRT fractionated scheduling. The Mucositis Observation Follow-up day 1 is the day following the last dose of IMRT.

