17. A 28 Day Safety Visit will occur 4 weeks (28 days) post last dose of radiation treatment (+5 day window). If the patient has an OM grade ≥ 2 , patient will continue with the Mucositis Observation Follow-up weekly visits until an OM grade of ≤ 1 is achieved. If the patient finished Combination Treatment with an OM grade ≤ 1 , the patient will return to clinic 28 days post IMRT (+ 5 days) for this 28 Day Safety Visit. Once the patient is assigned an OM grade ≤ 1 and has completed the 28 Day Safety Visit, the patient will proceed into Long Term Follow Up.
18. Long-Term Follow-Up may be performed via chart review. All procedures performed during the follow-up period should be recorded as Concomitant Procedures. Patients should continue to be followed monthly if experiencing an adverse event related to the investigational agent of RRx-001 until resolution, or event is assessed as a grade ≤ 2 .

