11.5 Tumor Assessments

Tumor assessments will be performed according to the schedule of assessments. The patient's tumor response will be assessed using RECIST v1.1 [Eisenhauer et al. 2009] until progression, start of next therapy or until end of Long Term Follow-up, whichever comes first [Appendix B]. When measurable disease is not present (e.g. post-operative patients), RECIST v1.1 assessment is not performed until measurable disease presents (this is considered progression and no further assessments will be done) or start of next therapy. Tumor status information will be collected and will include disease progression, and survival. During the follow up period, data will be collected at standard of care intervals, i.e., month 3 (\pm 7 days) and also at months 6, 9 and 12 (each \pm 14 days) following the last day of combination therapy to document start date of subsequent therapies.

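### Section 13.3 counts only radiographic RECIST progression or death as PFS events, so a survivor whose recurrence is found clinically and treated before a qualifying scan is informatively censored

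*Combined protocol and SAP*

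**What the plan says.** The synopsis and Section 5 make the long-term effect of RRx-001 on tumour response a safety objective. Section 13.3 contains the only time-to-event tumour analysis, a Kaplan-Meier description of PFS.

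- **Event (Section 13.3).** PFS runs from registration to the "first radiographic documentation of objective progression (per RECIST v1.1") or to death if that comes first.
- **Censoring (Section 13.3).** "Subjects still alive without progressive disease at the time of analysis will be censored". The date used is the "last" such observation in this sense: patients are "censored on the date of the last objective progression-free observation prior to the start of subsequent anti-cancer therapy".
- **End of RECIST reading (Section 1.2, footnotes 11 and 12; Section 11.5).** Reading continues until progression or the start of next therapy. Footnote 11 and Section 11.5 also end it at the close of the 12-month follow-up.
- **No measurable disease (Section 1.2, footnotes 11 and 12; Section 11.5).** "When measurable disease is not present (e.g. post-operative patients), RECIST v1.1 assessment is not performed until measurable disease presents (considered PD"), or until next therapy starts.
- **Conduct of follow-up (Section 1.2).** Imaging follows institutional standards. Footnote 18 adds that "Long-Term Follow-Up may be performed via chart review". Laryngopharyngoscopy is recommended but optional (footnote 3), and the table appears to mark it at the long-term visits.
- **Other tumour data.** The synopsis lists overall tumour response by RECIST or by criteria the site prefers. Section 13.3 tabulates response by arm at each follow-up visit. Section 11.5 collects progression and survival status and the start dates of later therapies.

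**The concern.** Radioprotection of normal mucosa is useful only if the tumour is not protected as well, so the tumour-safety data carry weight even in an exploratory study. In head and neck cancer a local recurrence can be seen or biopsied before any scan documents it. Under the plan such a finding is not a PFS event. If new therapy then starts, RECIST reading ends and the patient is censored at a date before the failure. The censoring is caused by the outcome being measured, so the Kaplan-Meier assumption that censored patients resemble those still at risk fails, and the curve sits too high. How far it is off depends on how each site images its patients, which the protocol leaves to local practice. With about 10 patients per arm, one event reclassified in this way is a large share of an arm's total.

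**Working it through.** **Step 1. Follow one patient through the rules.** A patient has a local recurrence confirmed by biopsy, begins salvage therapy before any scan that meets RECIST progression, and is alive at analysis.

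1. The biopsy is not radiographic RECIST progression, so it is not an event.
2. Next therapy has started, so RECIST reading stops and no later scan can supply the event.
3. The patient is alive without RECIST progression, so the censoring sentence applies, and the date falls before the new therapy.

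The result is a failure recorded as a censored, progression-free observation. If the patient later dies, the text appears to count the death, though late. Section 13.3 does not say how death after new therapy is handled.

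**Step 2. Size within an arm.** The documents state no PFS rate, event count, hazard ratio or margin, so there is no figure of the plan's own to reproduce. The inputs are assumptions: true 12-month event probability *p*, share *f* of failures censored instead of counted, constant hazard, and no later death among the lost failures.

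If lost failures are censored at about the time of failure, the observed hazard is (1 − *f*) times the true one:

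observed PFS = (1 − *p*)^(1 − *f*)

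With *p* = 0.20:
- *f* = 0.25: 0.8^0.75 = 84.6%
- *f* = 0.50: 0.8^0.50 = 89.4%

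The plan censors earlier than the failure. The extreme case is censoring the lost failures at time zero, which gives observed PFS = 1 − *p*(1 − *f*)/(1 − *pf*):
- *f* = 0.25: 1 − 0.15/0.95 = 84.2%
- *f* = 0.50: 1 − 0.10/0.90 = 88.9%

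So the exact censoring date hardly changes the result.

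For a wider range, the observed event probability 1 − (1 − *p*)^(1 − *f*) is:

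| True *p* | *f* = 0.2 | *f* = 0.4 | *f* = 0.6 |
|---|---|---|---|
| 0.15 | 0.122 | 0.093 | 0.063 |
| 0.25 | 0.206 | 0.159 | 0.109 |
| 0.40 | 0.335 | 0.264 | 0.185 |

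The relative understatement runs from about 16% (0.40 read as 0.335) to 58% (0.15 read as 0.063).

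**Step 3. Event counts.** With 10 patients and *p* = 0.20, 10 × 0.20 = 2 events are expected per arm. Losing 25% to 50% leaves 1.5 to 1.0.

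**Step 4. Between arms.** If *f* is the same in both arms, both hazards are multiplied by (1 − *f*) and the hazard ratio is unchanged. The absolute gap narrows. Take assumed event probabilities of 0.20 (control) and 0.40 (active) with *f* = 0.4. They read 1 − 0.8^0.6 = 0.125 and 1 − 0.6^0.6 = 0.264, so a gap of 0.20 reads as 0.139. In two arms of 10, 6 expected events become 6 × 0.6 = 3.6.

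**Step 5. Patients without measurable disease.** Prior surgery is allowed with no stated cap. For these patients "RECIST v1.1 assessment is not performed until measurable disease presents". The general censoring rule refers to an objective progression-free observation. It does not say which assessment serves when there are no RECIST reads, and it gives no fallback date.

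**The case against.** The strongest case against is that little is truly lost and PFS is not the only place to look.

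- Death is an event, newly measurable disease is expressly progression, and a clinically found recurrence that is scanned before next therapy is still captured. This stands. The gap is confined to survivors treated before a qualifying scan, and the documents do not show how often that happens. Allowing chart review does not exclude scans.
- PFS is not among the synopsis endpoints and has no formal comparison. The listed tumour endpoint admits site criteria, response is tabulated by visit, and progression, survival and later therapies are collected. This also stands: harm could surface elsewhere. None of it supplies the missing event in the one time-to-event analysis, and no rule links those data to PFS.
- A shift of 5 to 9 percentage points is less than one patient in an arm of 10, where an exact 95% interval around 8 of 10 is roughly 44% to 97%. True, but imprecision does not remove a bias of known direction.
- Treating new therapy as an event or as censoring is a choice of estimand. Agreed, which is why a sensitivity analysis is enough.

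Two stronger readings are tempting and should be resisted. A reader might infer that post-operative patients get no tumour assessment, or that those who never recur must be censored at registration, which would understate PFS. The text suspends the RECIST assessment, not imaging, which continues by institutional standards. The censoring sentence asks for an objective observation, not a RECIST read, so a clear scan can serve. No section censors at registration. What remains is an unnamed censoring assessment, not a second bias of known size.

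**Conclusion.** The point holds for a defined group: patients alive at analysis whose recurrence is established by examination, endoscopy or biopsy and treated before a scan meets RECIST progression. Followed exactly, the plan censors them informatively, and PFS within the arm is biased upward. The illustrative size is a true 80% at 12 months reading about 85% to 89%. It rests on an assumed 80%, an assumed 25% to 50% of failures lost, a constant hazard and no later deaths among those lost. The documents give none of these inputs.

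A reader might go further and infer that the rule will hide tumour harm caused by RRx-001. The documents do not support that. Equal loss in all arms neither creates nor reverses a difference, nothing shows that detection differs by arm, and other tumour data are tabulated. What can be said is that the rule removes events from arms with very few, in an open-label trial where the route to detection is left to sites. In an exploratory study this is worth correcting, mainly because the correction is cheap.

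**What to change.** Keep the RECIST-based PFS as written and add to Section 13.3:

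1. A pre-specified sensitivity analysis of PFS that also counts as events (a) clinically or pathologically confirmed recurrence and (b) the start of new anti-cancer therapy given for recurrence, each at its own date.
2. A summary by arm of the start of next anti-cancer therapy.
3. For patients without measurable disease, a censoring date equal to the last imaging or examination showing no recurrence.
4. One sentence on how death after new therapy is handled.

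Section 11.5 already collects progression and survival status and the start of later therapies, and footnote 18 of Section 1.2 has follow-up procedures recorded. The documents do not require the reason for new therapy or the basis on which a recurrence was called, so one extra data field may be needed. The downside is that some clinically called recurrences are less certain than imaged ones. That is the reason to place them in a sensitivity analysis beside the RECIST result and not in its place.
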